3.2 Post Study Access to Study

At the end of the 156 week study period, the Sponsor will not continue to provide Sponsor-supplied study drug to subjects/investigators unless the Sponsor chooses to extend the study. The investigator should ensure that the subject receives appropriate standard of care to treat the condition under study.

3.3 Study Population

For entry into the study, the following criteria MUST be met.

3.3.1 Inclusion Criteria

1. Signed Written Informed Consent

- a) Subjects (or designee) must be willing and able to give signed and dated written informed consent.

2. Target Population

- a) Subjects with T2DM with inadequate glycemic control, defined as a central laboratory HbA1c $\geq 7.5\%$ and $\leq 10.5\%$ obtained at the screening visit.
 - i) Note: The proportion of subject with HbA1c 7.5 % - 8.5 % will be capped at 40%.
 - ii) Note: At Week -2 (Lead-In), a qualification check will be performed and subjects will be included if their FPG is ≤ 270 mg/dL. A re-test will be permitted within 7 days if the initial result was > 270 mg/dL but < 300 mg/dL. Subjects will be excluded if the mean value of the Week -2 (Lead-In) result and the re-test result is > 270 mg/dL.
- b) Subjects should be taking the same daily dose of metformin ≥ 1500 mg for at least 8 weeks prior to the enrollment visit and must not take any other antihyperglycemic therapy for more than 14 days (consecutive or not) during 12 weeks prior to screening.
- c) BMI 20.0 to 45.0 kg/m² (inclusive) at the enrollment visit.
- d) Subject Re-enrollment: This study permits the re-enrollment of a subject who has been discontinued from the study as a pre-treatment failure (ie, subject has not been randomized / has not been treated). If re-enrolled, the subject must be re-consented.

Inclusion criteria at randomization (Visit 3, based on laboratory results from Visit 2):

- a) FPG ≤ 270 mg/dL (≤ 15 mmol/L).

For inclusion in the MRI-PDFF sub-study and/or CGM sub-study, subjects must fulfill the following criteria:

- b) Provision of informed consent for the MRI-PDFF and/or CGM sub-study.
- c) BMI 20.0 to 40.0 kg/m² (inclusive) at the enrollment visit and upper weight of 140 kg max (MRI-PDFF sub-study only).

If a subject declines to participate in the MRI-PDFF sub-study or CGM sub-study, there will be no consequences for the subject's participation in the main study. The subject will not be excluded from other aspects of the study described in this Clinical Study Protocol, as long as proper consent is obtained.

3. Age and Reproductive Status

- a) Males and females, aged ≥ 18 years old at the time of the screening visit.
- b) Women of childbearing potential (WOCBP) must have a negative serum or urine pregnancy test (minimum sensitivity 25 IU/L or equivalent units of HCG) within 24 hours prior to the start of study drug.
- c) Women must not be breastfeeding
- d) WOCBP must agree to follow instructions for method(s) of contraception for the duration of treatment with study drugs: saxagliptin, and dapagliflozin, and glimepiride plus 5 half-lives of study drugs: saxagliptin, dapagliflozin, and glimepiride (30 days) plus 30 days (duration of ovulatory cycle) for a total of 60 days post-treatment completion.
- e) Males who are sexually active with WOCBP must agree to follow instructions for method(s) of contraception for the duration of treatment with study drugs: saxagliptin, dapagliflozin, and glimepiride plus 5 half-lives of the study drug (30 days) plus 90 days (duration of sperm turnover) for a total of 120 days post-treatment completion.
- f) Azoospermic males and WOCBP who are continuously not heterosexually active are exempt from contraceptive requirements. However they must still undergo pregnancy testing as described in this section.

Investigators shall counsel WOCBP and male subjects who are sexually active with WOCBP on the importance of pregnancy prevention and the implications of an unexpected pregnancy. Investigators shall advise WOCBP and male subjects who are sexually active with WOCBP on the use of highly effective methods of contraception. Highly effective methods of contraception have a failure rate of $< 1\%$ per year when used consistently and correctly.

At a minimum, subjects must agree to the use of one method of highly effective contraception as listed below:

HIGHLY EFFECTIVE METHODS OF CONTRACEPTION

- Progestogen only hormonal contraception associated with inhibition of ovulation.
- Hormonal methods of contraception including combined oral contraceptive pills containing a combination of estrogen + progesterone, vaginal ring, injectables, implants and intrauterine devices (IUD).
- Nonhormonal IUDs
- Bilateral tubal occlusion
- Vasectomised partner with documented azoospermia 90 days after procedure
- Vasectomized partner is a highly effective birth control method provided that partner is the sole sexual partner of the WOCBP trial participant and that the vasectomized partner has received medical assessment of the surgical success.
- Intrauterine hormone-releasing system (IUS)

- Complete Abstinence*

*Complete abstinence as defined as complete avoidance of heterosexual intercourse is an acceptable form of contraception for all study drugs. This also means that abstinence is the preferred and usual lifestyle of the patient. This does not mean periodic abstinence (eg, calendar, ovulation, symptothermal, profession of abstinence for entry into a clinical trial, post-ovulation methods) and withdrawal, which are not acceptable methods of contraception. Subjects who choose complete abstinence are not required to use a second method of contraception, but WOCBP subjects must continue to have pregnancy tests. Acceptable alternate methods of highly effective contraception must be discussed in the event that the subject chooses to forego complete abstinence.

3.3.2 Exclusion Criteria

4. Target Disease Exceptions

- a) Clinical diagnosis of type I diabetes, known diagnosis of mature onset diabetes of youth (MODY), secondary diabetes mellitus, or diabetes insipidus.
- b) History of diabetic ketoacidosis

5. Medical History and Concurrent Diseases

- a) Any of the following cardiovascular/vascular diseases within 3 months of the enrollment visit:
 - i) Myocardial infarction
 - ii) Cardiac surgery or revascularization (coronary artery bypass surgery [CABG]/percutaneous transluminal coronary angioplasty [PTCA])
 - iii) Unstable angina
 - iv) Unstable congestive heart failure (CHF)
 - v) Transient ischemic attack (TIA) or significant cerebrovascular disease
 - vi) Unstable or previously undiagnosed arrhythmia
 - vii) Congestive heart failure, defined as New York Heart Association (NYHA) Class III and IV, unstable or acute congestive heart failure and/or known left ventricular ejection fraction of $\leq 40\%$.

Note: eligible patients with congestive heart failure, especially those who are on diuretic therapy, should have careful monitoring of their volume status throughout the study.

- b) Renal disease:
 - i) History of unstable or rapidly progressing renal disease

- ii) Impairment of renal function (defined as $\text{CrCl} < 60 \text{ mL/min}$ [estimated by Cockcroft-Gault] or serum creatinine [SCr] $\geq 1.5 \text{ mg/dL}$ in males or $\geq 1.4 \text{ mg/dL}$ in females).
 - iii) Hematuria (confirmed by microscopy at screening) with no explanation as judged by the investigator up to randomization. If bladder cancer is identified, subjects are not eligible to participate.
- c) Hepatic diseases:
- i) Severe hepatic insufficiency and/or significant abnormal liver function defined as aspartate aminotransferase (AST) $> 3x$ upper limit of normal (ULN) and/or alanine aminotransferase (ALT) $> 3x$ ULN.
 - ii) Serum total bilirubin $> 2.0 \text{ mg/dL}$ ($> 34.2 \mu\text{mol/L}$).
 - iii) Severe hepatic disease, including chronic active hepatitis. Positive serologic evidence of current infectious liver disease, including subjects who are positive for hepatitis B viral antibody IgM, hepatitis B surface antigen, and hepatitis C virus antibody.
- d) Pancreatic disease
- i) History of, or current, acute or chronic pancreatitis.
- e) Hematological and oncological disease/conditions:
- i) History of hemoglobinopathy, with the exception of sickle cell trait (SA) or thalassemia minor; or chronic or recurrent hemolysis.
 - ii) Malignancy within 5 years of the screening visit (with the exception of treated basal cell or treated squamous cell carcinoma).
 - iii) History of bladder cancer or history of radiation therapy to the lower abdomen or pelvis at any time.

6. Physical and Laboratory Test Findings

- a) Hemoglobin $\leq 11.0 \text{ g/dL}$ (110 g/L) for men; hemoglobin $\leq 10.0 \text{ g/dL}$ (100 g/L) for women.
- b) An abnormal TSH value at enrollment will be further evaluated for free T4. Subjects with abnormal free T4 values will be excluded. (Note: A one-time retest of TSH may be allowed, as determined by the investigator, after a minimum of 6 weeks following the adjustment of thyroid hormone replacement therapy in subjects who have had a prior diagnosis of a thyroid disorder and who are currently receiving thyroid replacement therapy. Such cases should be discussed with the Sponsor prior to re-testing. The subject must have all enrollment procedures and laboratory assessments performed as part of this re-test, and all of these must meet enrollment eligibility criteria. The subject's number will however remain the same as initially assigned.)
- c) Any clinically significant abnormality identified on physical examination, ECG or laboratory tests, which in the judgment of the investigator would compromise the subjects' safety or successful participation in the clinical study.

7. Allergies and Adverse Drug Reaction

- a) Subjects who have contraindications to therapy as outlined in the saxagliptin and dapagliflozin Investigator Brochures, the local saxagliptin or dapagliflozin or glimepiride or metformin package insert, including current treatment with potent cytochrome P450 3A4/5 inhibitors (in countries where dose adjustment would be required by the local saxagliptin label).

8. Other Exclusion Criteria

- a) Prisoners or subjects who are involuntarily incarcerated.
- b) Subjects who are compulsorily detained for treatment of either a psychiatric or physical (eg, infectious disease) illness.
- c) Subjects on a commercial weight loss program with ongoing weight loss, or on an intensive exercise program.
- d) Subjects who are taking any prescription or over-the-counter (OTC) medications for weight loss within 3 months of the screening visit.
- e) History of any bariatric surgical procedure, Nissen fundoplication, or other procedures that can affect endogenous GLP-1 levels prior to screening.
- f) Replacement or chronic systemic corticosteroid therapy, defined as any dose of systemic corticosteroid taken for > 4 weeks within 3 months prior to the Day 1 visit
 - i) NOTE: Topical or inhaled corticosteroids are allowed
- g) Any unstable endocrine, psychiatric or rheumatic disorders as judged by the investigator
- h) Volume depleted subjects. Subjects at risk for volume depletion due to co-existing conditions or concomitant medications, such as loop diuretics, should carefully monitor their volume status.
- i) Subject with any condition which, in the judgment of the investigator, may render the subject unable to complete the study or which may pose a significant risk to the subject or subject suspected or with confirmed poor protocol or medication compliance.
- j) Subject is currently abusing alcohol or other drugs or has done so within the last 6 months prior to the screening visit.
- k) Subject is a participating investigator, study coordinator, employee of an investigator or immediate family member of any of the aforementioned.
- l) Involvement in the planning and/or conduct of the study (applies to both Sponsor staff and/or staff at the study site).
- m) Previous randomization in the present study.
- n) Administration of any other investigational drug within 30 days of the screening visit
- o) Clinical conditions or clinically significant abnormalities, in any laboratory value(s) collected after screening and prior to randomization which, in the investigator's judgment, should preclude entry into the treatment period.

Eligibility criteria for this study have been carefully considered to ensure the safety of the study subjects and that the results of the study can be used. It is imperative that subjects fully meet all eligibility criteria.

3.3.3 Women of Childbearing Potential

A woman of childbearing potential (WOCBP) is defined as any female who has experienced menarche and who has not undergone surgical sterilization (hysterectomy or bilateral oophorectomy) and is not postmenopausal. Menopause is defined as 12 months of amenorrhea in a woman over age 45 years in the absence of other biological or physiological causes. In addition, females under the age of 55 years must have a serum follicle stimulating hormone, (FSH) level > 40 mIU/mL to confirm menopause.

*Females treated with hormone replacement therapy (HRT) are likely to have artificially suppressed FSH levels and may require a washout period in order to obtain a physiologic FSH level. The duration of the washout period is a function of the type of HRT used. The duration of the washout period below are suggested guidelines and the investigators should use their judgment in checking serum FSH levels. If the serum FSH level is > 40 mIU/ml at any time during the washout period, the woman can be considered postmenopausal:

- 1 week minimum for vaginal hormonal products (rings, creams, gels)
- 4 week minimum for transdermal products
- 8 week minimum for oral products

Other parenteral products may require washout periods as long as 6 months.

3.4 Concomitant Treatments

3.4.1 Prohibited and/or Restricted Treatments

Once enrolled, subjects may not receive any of the following for the duration of the screening (qualification period), lead-in, double-blinded short-term and subject- and site-blinded long-term treatment periods:

- Treatment with sulfonylureas other than IMP, pioglitazone, rosiglitazone, glucagon-like peptide-1 (GLP-1) receptor agonists, dipeptidyl peptidase-4 (DPP-4) other than IMP, and any sodium glucose co-transporter 2 (SGLT2) inhibitors other than IMP is not permitted for the duration of the study. If rescue therapy is required and a subject refuses treatment with insulin or is not a candidate for insulin, other diabetic agents can be considered as second-line rescue therapy ([Section 3.5.2](#)).
- Insulin therapy within one year of enrollment (with the exception of insulin therapy during a hospitalization or use in gestational diabetes), other than as a first-line rescue therapy ([Section 3.5.2](#)).
- Current treatment with potent cytochrome P450 3A4/5 inhibitors (in countries where dose adjustment would be required by the saxagliptin label).

- Administration of any other investigational drug or participation in any interventional clinical studies 30 days prior of planned screening to this study.
- Newly initiated treatment with any systemic corticosteroid therapy (including oral and injectable) that will involve ≥ 5 days of therapy is not permitted (inhaled and topical are allowed). The Sponsor Medical Monitor should be consulted prior to beginning therapy with corticosteroids for subjects who require systemic corticosteroid treatment.

3.4.2 Other Restrictions and Precautions

- Subjects must comply with their prescribed dosing regimen to preserve study integrity and ensure subject safety.
- Subjects should be cautioned that any new prescription, OTC or herbal/nutritional therapies should be discussed thoroughly with the investigator as concomitant use could result in alterations to their glycemic control and may place them at risk for significant hypoglycemic episodes.
- Subjects must make every attempt to adhere to the diet and exercise counseling and to the study flow chart/time and event schedule (see [Section 5.1](#))
- Women of child-bearing potential must immediately contact the investigator if they suspect they might be pregnant and if they have changed or plan to change their birth control method (see [Section 6.5](#)).

3.5 Discontinuation of Subjects following any Treatment with Study Drug

Subjects MUST discontinue IMP (and non-IMP at the discretion of the investigator) for any of the following reasons:

- Subject's request to stop study treatment.
- Any clinical adverse event (AE), laboratory abnormality or intercurrent illness which, in the opinion of the investigator, indicates that continued participation in the study is not in the best interest of the subject.
- Termination of the study by the Sponsor.
- Loss of ability to freely provide consent through imprisonment or involuntarily incarceration for treatment of either a psychiatric or physical (eg, infectious disease) illness.
 - Unblinding a subject for any reason (emergency or non-emergency).
- Severe non-compliance to protocol, as judged by the investigator and/or Sponsor.
- Safety reasons as judged by the investigator and/or Sponsor.
- Incorrect enrollment (ie, the subject does not meet the require inclusion/exclusion criteria) for the study.
- Pregnancy.
- CrCl < 60 mL/min (estimated by Cockcroft-Gault), with a repeat confirmation test result 3 to 7 days following the receipt of the initial result. Subjects with a CrCl < 60 ml/min will have background therapy metformin withheld until the confirmatory repeat CrCl is received.

- If the repeat CrCl > 60 ml/min the subject may resume background therapy metformin.
- If the repeat CrCl < 60 ml/min the subject must be discontinued from all study medication.
- Subjects with a central laboratory ALT and/or AST > 3xULN will be scheduled for a follow-up visit within 3 days following the receipt of the result (see [Appendix 4](#) for further guidance). Subjects should be discontinued from study if the initial and repeat laboratory tests meet any of the following criteria:
 - ALT and/or AST are > 3x ULN and total bilirubin (TB) > 2x ULN.
 - ALT and/or AST are > 5x ULN for ≥ 14 consecutive days, at any time after initial confirmatory results.
 - ALT and/or AST are ≥ 10x ULN.

In the case of pregnancy, the investigator must immediately notify the Sponsor Medical Monitor/designee of this event. Study drug will be permanently discontinued in any subjects that become pregnant during the study; the study drug will be permanently discontinued in an appropriate manner (eg, dose tapering if necessary for subject safety).

All subjects who discontinue study drug should comply with protocol specified follow-up procedures as outlined in [Table 5.1-4](#). The only exception to this requirement is when a subject withdraws consent for all study procedures, including post-treatment study follow-up or loses the ability to consent freely (ie, is imprisoned or involuntarily incarcerated for the treatment of either a psychiatric or physical illness).

If study drug is discontinued prior to the subject's completion of the study, the reason for the discontinuation must be documented in the subject's medical records and entered on the appropriate Case Report Form (CRF) page.

3.5.1 Procedures for handling patients incorrectly enrolled or randomized

Subjects who fail to meet the inclusion/exclusion criteria must not, under any circumstances, be enrolled or randomized. There can be no exceptions to this rule.

Subjects who are incorrectly enrolled, but are not yet randomized, should be withdrawn from the study. The procedures included in the protocol for the discontinuation of such subjects must be followed. Study medication should be permanently stopped and the subject should be further treated according to the investigators judgment and local therapy tradition.

If a subject not meeting the study criteria is randomized in error, and if the error is identified after randomization, a discussion must occur between the Sponsor Medical Monitor and the investigator regarding whether to continue or discontinue the subject from the study. If agreement is reached, the subject should complete the study unless there are safety concerns or if the subject withdraws the consent. In situations in which an agreement cannot be reached, the subject should have the randomized therapy stopped and be discontinued from the study. The procedures included in the protocol for the discontinuation of such subjects must be followed.

The Sponsor Medical Monitor is to ensure all such contacts with the investigator and such decisions are appropriately documented.

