3 INVESTIGATIONAL PLAN

3.1 Study Design and Duration

Study CV181365 is an international, multicenter, randomized, double-blind, active-controlled, parallel-group Phase 3b study whose primary endpoint is the change from baseline in HbA1c with saxagliptin, in combination with dapagliflozin, on top of background therapy with metformin, compared to glimepiride as an adjunct to metformin monotherapy. The primary endpoint of HbA1c will be assessed at 52 weeks; however, the trial will continue for 156 weeks as a subject- and site-blinded extension.

Subjects with documented T2DM treated with metformin monotherapy will be enrolled. All subjects should be treated according to regional standards of care for diabetes.

Subjects must be receiving metformin in accordance with the product label for their country.

Approximately 440 subjects meeting all eligibility criteria at approximately 110 study sites will be randomized (1:1) to receive either saxagliptin co-administered with dapagliflozin or glimepiride.

Enrollment of subjects based on disease state, and geographic region will be monitored and may be capped to ensure adequate representation.

All potentially eligible subjects will undergo a screening visit. Each subject will sign an Informed Consent Form (ICF) prior to having any screening evaluations performed. Subjects who fulfill all eligibility requirements will enter into a 2-week screening period and a 2-week lead-in period, during which they will continue to take their background medication with at least 1500 mg metformin.

Approximately 2 weeks after entering the lead-in period, subjects will be expected to undergo a randomization visit. Subjects may withdraw prior to the randomization visit, or be withdrawn by study staff for any reason. At this visit, subjects will be re-evaluated by study staff to determine, if, after testing performed at the screening visit, after assessment of compliance, and any clinical changes that may have occurred during the run-in period, the subject remains eligible and committed to participation in the study. If for any reason, prior to or during the randomization visit, the subject is no longer eligible or interested in participating in the trial, he or she will be considered a run-in failure, will not be randomized, and will not have additional follow up.

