All subjects who discontinue from treatment should remain in the study and comply with protocol-specified follow-up procedures. The only exception to this requirement is when a subject withdraws consent for all study procedures or loses the ability to consent freely (ie, is imprisoned or involuntarily incarcerated for the treatment of either a psychiatric or physical illness).

Subjects lost to follow-up are defined by: 1) unable to reach the subject after three documented phone calls, fax, email or attempts to contact him/her through subject locator agencies (if allowed per national regulation); and 2) having sent one letter by registered/certified mail; all should be documented in the subject's medical records.

MRI-PDFF

A MRI-PDFF sub-study will be conducted at approximately 11 MRI sites in Europe. Approximately 60 (30 per arm) subjects from selected recruiting sites are expected to participate in the MRI-PDFF sub-study. Each subject participating in the MRI sub-study will be referred to a MRI site for MRI measurements. Several recruitment sites can refer subjects to one MRI site. Subjects participating in the MRI-PDFF sub-study will be required to provide informed consent. The date of these MRI assessments need not be the same as for Visit 1, but should be performed before Visit 3.

All subjects suitable for the study, including the MRI-PDFF sub-study, will be screened and recruited by the recruiting sites (sites treating subjects with T2DM). The recruiting investigator will be the main point of contact for the subject and also responsible for the documentation of study data within the eCRF. All subjects should have MRI visits scheduled to coincide with randomization, Week 52, and Week 122.

All MRIs will be sent for central evaluation to a core laboratory. No local reading will be performed. The results will be kept blinded to recruiting sites, the MRI sites, the subjects, and the Sponsor until the study is completed.

Continuous Glucose Monitoring (CGM)

[figure not shown]

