3.6 Post-Study Drug Study Follow up

In this study, safety is a key endpoint of the study. Post-study follow-up is of critical importance and is essential to preserving subject safety and the integrity of the study. Subjects who discontinue study drug must continue to be followed for collection of outcome and/or survival follow-up data as required, and in line with [Section 5](#), until death or the conclusion of the study.

Therefore, all subjects who discontinue IMP in the 52 week double-blinded short-term treatment period or in the long-term treatment period should be asked to continue study participation for each scheduled visit for the remaining length of the study and complete all procedures as outlined in [Section 5 \[Table 5.1-4\]](#) study flowchart, with the exception of study drug management. If continued study participation according to the protocol schedule is not possible, the investigator should contact the Sponsor to discuss alternatives (eg, return to the clinic 4 weeks after discontinuation of study drug to perform the Week 56 post-treatment follow-up procedures as outlined in [Section 5 \[Table 5.1-4\]](#) study flowchart or be contacted by telephone 4 weeks after discontinuation of study drug to evaluate the following safety assessments: AEs and hypoglycemia events. Please note that after the discontinuation of study drug, the management of the subject's diabetes will be under the care and direction of the investigator.)

The only exception to any of these follow-up methods are when a subject withdraws consent for all study procedures, including post-treatment study follow-up or loses the ability to consent freely (ie, is imprisoned or involuntarily incarcerated for the treatment of either a psychiatric or physical illness).

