For subjects who are discontinued from study medication as a result of sustained elevated liver safety abnormalities, as described in [Section 3.5](#), additional blood sampling must be done within 3 days of the confirmed laboratory results (see [Appendix 4](#)), in conjunction with an Early Treatment Discontinuation (End-of-Treatment) visit, in addition to the procedures noted above. A referral consultation to a hepatologist or gastroenterologist (specializing in liver abnormalities) should be obtained. **Any additional tests and/or examinations should be carried out at the discretion of the investigator. Any further investigations and laboratory results for subjects with abnormal laboratory values at the follow-up visit should be made available to the Sponsor upon request.**

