5.3.8 Supplemental Visits

5.3.8.1 Rescue or Early Treatment Discontinuation Visit

Subjects rescued during or discontinued from the short-term double-blind treatment period

Any subject who qualifies for rescue or discontinues from the short-term double-blind treatment period must have all Rescue/Early Treatment Discontinuation (ETD) visit procedures performed at the time of study discontinuation or rescue. The IVRS must be called to record the subject status (ie, rescue, or discontinuation status). All subjects who are rescued or who discontinue study drug should remain in the study and follow the visit schedule.

- For subjects qualifying for rescue PRIOR to Week 52, Rescue/ETD procedures will be performed and the subject will then continue in the treatment period according to the regular visit schedule. The Rescue/ETD supplemental eCRF will need to be completed to collect rescue-related endpoint data. A Week 52/Rescue/ETD visit laboratory kit will need to be used to collect the Rescue Visit blood and urine samples.
- Subjects who discontinue study medication during the short-term double-blind treatment period should have all ETD procedures performed (Rescue/ETD visit). The Rescue/ETD eCRF will also need to be completed and a Week 52/Rescue/ETD visit laboratory kit will need to be used to collect the ETD Visit blood and urine samples. Subjects will then continue in the study according to the regular visit schedule, including the long-term subject- and site-blinded treatment period.

Subjects rescued during or discontinued from the long-term subject- and site-blinded treatment period

Any subject who qualifies for rescue or discontinues from the long-term subject- and site-blinded treatment period must have all Rescue/Early Treatment Discontinuation (ETD) visit procedures performed at the time of study discontinuation or rescue. The IVRS must be called to record the subject status (ie, rescue, or discontinuation status). All subjects who are rescued or who discontinue study drug should remain in the study and follow the long-term visit schedule.

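### Protocol 3.5.1 can be read as ending follow-up for a subject randomised in error when no agreement is reached, contrary to the plan's general follow-up rule

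*Protocol*

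**What the plan says.** Protocol 3.5.1 deals separately with three groups. Subjects wrongly enrolled but not yet randomised are withdrawn. Subjects randomised in error whose case is agreed between the Medical Monitor and the investigator normally complete the study. Where there is no agreement, "the subject should have the randomized therapy stopped and be discontinued from the study". The paragraph then adds: "The procedures included in the protocol for the discontinuation of such subjects must be followed". It names no section.

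The general rule for subjects who stop drug appears in several places:

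- Protocol 3.1: "All subjects who discontinue from treatment should remain in the study and comply with protocol-specified follow-up procedures".
- Protocol 3.5 sends everyone who stops study drug to Table 5.1-4. "The only exception to this requirement is when a subject withdraws consent for all study procedures", or loses the capacity to consent freely.
- Protocol 3.6: "Subjects who discontinue study drug must continue to be followed for collection of outcome and/or survival follow-up data as required".
- Protocol 5.3.8.1: "All subjects who are rescued or who discontinue study drug should remain in the study and follow the visit schedule".
- SAP 2.1 and 6.1 keep subjects who stop treatment on the same visit schedule as those still on it.

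Protocol 3.5 also lists incorrect enrolment among the reasons for stopping IMP. SAP 6.3.3 defines the ITT set as randomised subjects with at least one dose and does not remove anyone for ineligibility.

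**The concern.** The no-agreement sentence orders two acts joined by ‘and’: stop therapy, and leave the study. If the second act means what it says, a randomised and treated subject leaves follow-up for a reason that is not among the stated exceptions. That subject still counts in the ITT set, so the later values become missing data created by the protocol itself.

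Two things would be at stake. The first is off-drug HbA1c, which the SAP uses in analyses that include values after drug is stopped. The second is later safety follow-up in subjects who failed an entry criterion; those criteria include renal, hepatic and pancreatic exclusions.

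**Working it through.** The check is mainly a comparison of texts.

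**Step 1. Does any exception cover this subject?** Protocol 3.1, 3.5 and 3.6 and SAP 2.1 give the same two exceptions: withdrawal of consent to all procedures, and loss of the ability to consent freely. Ineligibility is not one of them. Because 3.5 lists incorrect enrolment as a reason to stop IMP, the follow-up rule in 3.5 applies to that subject. Sections 3.5 and 3.5.1, read literally, give different instructions for the same person.

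**Step 2. Does the next sentence of 3.5.1 resolve it?** Not clearly. The same sentence is used earlier in 3.5.1 for subjects not yet randomised. Under Protocol 3.1 a subject found ineligible by the randomisation visit "will be considered a run-in failure, will not be randomized, and will not have additional follow up". So the sentence is compatible both with follow-up and with none.

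**Step 3. Is the phrase redefined anywhere?** For the liver criteria it is. Protocol 3.5 speaks of discontinuing the subject from study, and 5.3.4 restates this: "For subjects who are discontinued from study medication as a result of sustained elevated liver safety abnormalities". Nothing does the same for 3.5.1.

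**Step 4. What would still be collected on the literal reading?** The early discontinuation visit (Protocol 5.3.8.1) and SAEs within 30 days of the last dose (6.1.1). Protocol 5.8.5 also permits, but does not require, contact for vital status and safety.

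**Step 5. What could be lost?** Table 5.1-4, footnote a, sets office visits at Weeks 28, 52, 104 and 156, each with HbA1c and a blood safety panel, and phone assessments at the other scheduled times. The number of office visits lost per subject is at most:

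| Drug stopped | Office visits remaining |
|---|---|
| before Week 28 | 4 |
| Week 28 to before Week 52 | 3 |
| Week 52 to before Week 104 | 2 |
| Week 104 to before Week 156 | 1 |

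**Step 6. Which analyses use those HbA1c values?**

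- Primary Week 52 model: essentially none of them. SAP 7.5.2 and 8.3.1 exclude HbA1c taken after the 8th day following the last dose.
- Week 52 repeat of the primary model on all values, on or off drug (SAP 7.5.2): Weeks 28 and 52.
- Week 52 return-to-baseline imputation (SAP 7.5.3.1): Week 52 only. An observed off-drug change would be replaced by a draw from N(0, v_imp), where v_imp = (1 + 1/N_c) v_c.
- Week 156 repeated measures analysis on all values (SAP 7.5.2): all four visits.

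**Step 7. Does any stated number change?** No. The sample size reproduces: n = 2(1.960 + 1.282)² × 1.1² / 0.35² = 207.6, so 208 evaluable per arm; 208/0.95 = 218.9, so 219 against the stated 220. With 220 × 0.95 = 209 evaluable per arm, power is 0.902.

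As a scale only, suppose an all-values analysis lost a further 1, 2, 4 or 11 subjects per arm entirely. Power would be 0.901, 0.899, 0.896 or 0.886. These counts are assumptions, and 11 (5% of 220) is far above anything the pathway suggests. The sums also treat each lost subject as contributing nothing, although earlier values would remain in a repeated measures model.

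**The case against.** The best reply is that this is loose wording and not a removal rule. The protocol uses study-discontinuation language for stopping drug elsewhere: in 3.5.3 on severe hypoglycaemia, in 6.5 on pregnancy, and in 5.3.8.1, where the same paragraph goes on to keep these subjects in the study. Section 3.5.1 sits under 3.5, directly after the follow-up rule. For a treated subject, the discontinuation procedures it invokes can reasonably be taken as those of 3.5, 3.6 and 5.3.8.1, all of which include follow-up.

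Much of this stands. Loss of follow-up is a plausible literal reading, not a certainty. But the instances of loose usage show ambiguity; they do not cancel the second act in 3.5.1, which is named separately from stopping therapy.

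The reply is also right on scale. The pathway needs a randomisation error, later detection and a deadlock. Four visits is a ceiling, and Protocol 3.6 already allows reduced follow-up where the full schedule is not possible.

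A reader might infer that all safety follow-up stops at once. The documents do not support that, given the early discontinuation visit and the 30-day SAE collection.

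**Conclusion.** The inconsistency is real but minor, and worth correcting because the correction is so small. As written, 3.5.1 gives a site textual grounds to end visits for a treated subject who remains in the ITT set, against the rule in both documents.

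The possible loss is limited to later off-drug HbA1c, used in the all-values analyses at Weeks 52 and 156 and in the Week 52 return-to-baseline imputation, and to later safety visits. The effect on results cannot be quantified, because the documents give neither the number of no-agreement subjects nor their off-drug HbA1c. That the number is very small is a judgement from how rare the pathway should be.

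A reader might go further and infer bias or lost power in the primary comparison. The documents do not support this: the primary model discards nearly all of these values whether or not they are collected, and 220 per arm with 90% power stands.

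**What to change.** Replace the no-agreement sentence in Protocol 3.5.1 with wording such as:

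> If no agreement is reached, the subject should discontinue IMP, complete the Early Treatment Discontinuation visit, and continue follow-up per Section 3.6 and Table 5.1-4, unless consent to all study procedures is withdrawn or the ability to consent freely is lost.

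Leave the incorrect-enrolment bullet in 3.5 as it is. Making it subject to 3.5.1 would turn a mandatory IMP stop into a conditional one. That is a substantive decision and is not needed here.

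The cost is one protocol sentence, with the IRB/IEC handling that Protocol 9.1.1 requires for a revision; it can go into the next amendment. The SAP, visit schedule and sample size do not change.
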